## Background

As detailed in the accompanying paper [1], the U@Uni intervention was initially trialled with the 2012 cohort of incoming undergraduate students to the University of Sheffield. The results of the trial indicated that the U@Uni intervention had a significant effect on smoking status at six-month follow-up, although the intervention did not significantly effect the other primary outcome variables (i.e., portions of fruit and vegetables, physical activity, units of alcohol).

Unfortunately, the original trial was compromised by a number of limitations that resulted in recruitment into the trial and engagement with the intervention being lower than expected; indeed, just 1% of the participants completed all three components of the intervention. This may have been due to four issues. First, the bespoke software platform that was developed to deliver the U@Uni intervention had a number of technical glitches. As a result, participants' experience of completing the baseline questionnaire and being directed to the intervention was less than optimal. What was intended to be a seamless process was experienced as a series of discreet steps with subsequent drop-out at each step. For example, after completing the baseline questionnaire, participants in the intervention arm were directed to the U@Uni login page where they had to enter some registration details before completing the self-affirmation manipulation. After completing self-affirmation manipulation, participants had to login a second time in order to access the intervention material. Second, as a result of efforts to try to correct the technical glitches, the recruitment emails were sent a week later than intended, which meant that potential participants received the initial recruitment emails only two weeks before the start of the first semester (i.e., only one week before "Freshers' Week"). This may have coincided with a particularly busy period of time for many potential participants which may have dampened recruitment. Third, the baseline questionnaire was time-consuming to complete (approximately 20 minutes) due to the large number of items needed to assess the primary and secondary outcomes variables. Indeed,

approximately 9% of those who started the questionnaire failed to complete it. Fourth, intervention participants had complete control over the extent and type of intervention material that they viewed. For example, intervention participants could choose which health behaviours and which belief-based messages to view and whether or not to make plans. However, this may also have reduced engagement as intervention participants could choose not to view any messages or make any plans.

With these limitations in mind, a number of changes will be made to the study protocol and a repeat trial will be conducted. First, the intervention will be delivered using the LifeGuide open-source software platform [2]. LifeGuide has been specifically designed for researchers to develop, deliver and evaluate online health behaviour interventions. It allows participants to complete baseline measures, be randomly allocated to arms, and access intervention material all within the same website. As a result, transitions between the various tasks are experienced by participants as seamless with reduced opportunity to exit (e.g., by having to re-login). Second, the initial recruitment emails will be sent to potential participants four weeks before the start of the first semester (i.e., three weeks before “Freshers’ Week”). This will extend the recruitment period and ensure that potential participants are able to complete the baseline questionnaire well before starting university. Third, the baseline questionnaire will be shortened, where possible, through the use of brief measures of the primary outcome variables and removing measures of some of the secondary outcome variables. This will help to reduce questionnaire fatigue before participants are directed to the intervention material. Fourth, when visiting the intervention website, participants will be required to work through four short modules that will require them to choose at least one belief-based message to read and to make at least one plan for each health behaviour, before gaining access to the full intervention website. It is hoped that these changes will mean that the repeat trial is able to provide more accurate data on the efficacy of the intervention by ensuring that more participants are recruited into the trial and that intervention participants

view (i.e., engage with) the intervention material. This, in turn, should provide more precise estimates of the intervention effects and reduce decision uncertainty in the health economic modelling.

### **Principal Research Questions**

The primary research question is whether, compared to a measurement only control arm, an online digital intervention (“U@Uni LifeGuide”) delivered during the transition from school to university produces significant changes in the health behaviours (i.e., fruit and vegetable intake, physical activity, alcohol consumption, smoking) of young people six months after starting university. Additional research questions that will be addressed include whether the intervention: (i) changes health beliefs (and whether these changes mediate the effect of the intervention on the health behaviours), (ii) enhances health status, (iii) reduces health service usage, (iv) reduces recreational drug use, and (v) reduces BMI.

### **Method**

#### **Ethical Approval**

The study was approved by the Department of Psychology Research Ethics Committee at the University of Sheffield (no. 2013-665).

#### **Trial Registration**

Current Controlled Trials, ISRCTN07407344.

#### **Design**

Randomised controlled trial with 2 arms: (i) an online intervention targeting four health behaviours during the transition from school to university and (ii) measurement only control.

#### **Recruitment, Randomization and Allocation**

Incoming undergraduate students to the University of Sheffield ( $N \approx 5000$ ) will be sent an email one month before the start of semester 1 with information about the study and a link to the baseline questionnaire. On completion of the baseline questionnaire participants will

be randomly allocated to one of two arms using a random number generator (as part of the LifeGuide software). Participants in both arms of the trial will be sent emails with links to the follow-up questionnaires using SurveyGizmo one and six months after starting university. All participants will receive three automatic reminders to complete the questionnaires at each time point. Participants in the intervention arm will also be sent automatic email prompts to use the intervention website after initially accessing the intervention website and shortly before the start of their second semester at university. Participants will receive incentives to complete the questionnaires by being entered into £100 prize draws at each time point. Participants who complete all three questionnaires will receive a £10 gift voucher and will be entered into a further prize draw for an iPad mini.

### **Intervention**

After completing the baseline questionnaire, participants in the intervention arm will be directed to the online intervention that will combine three techniques from health psychology (self-affirmation, theory-based messages, and implementation intentions) to support the adoption of healthy behaviours at university. The intervention will be delivered using the open-access LifeGuide software platform.

Participants allocated to the intervention arm will first complete a self-affirmation task. They will be asked to provide details of their name, course, home town and main interests/hobbies before being asked to select their most important personal value from a list of 8 commonly held personal values (e.g., sense of humour, academic achievement; adapted from [3]) in a drop-down menu (or provide their own). Participants will also be asked to briefly provide one reason why the value is important to them. The resultant information will form part of the user's "profile" that will be displayed in the banner at the top of all pages of the intervention website. The profile will include the participant's name as well as the value they chose and the reason why it is important to them ("I value "X" because "Y") and will serve as a self-affirmation "booster" (i.e., to reaffirm participants whenever the website is

accessed). Participants will then be directed to complete four short modules on each of the four targeted health behaviours before gaining access to the full U@Uni website.

Module 1 will focus on exercising regularly at university. Participants will be presented with a list of the topic headings that contain the belief-based messages developed via formative research [4] and instructed to choose one topic (e.g., “Exercise improves your fitness”). They will then be directed to the intervention page containing the theory-based message that will include a mixture of text, videos of students talking about the targeted belief, and links to other related material. After viewing the page, participants will have the opportunity to either view another topic/message or proceed to the planner. On the planner page, participants will be presented with a brief video and text explaining the purpose and format of the planning exercise. They will be presented with an example of an implementation intention in an if-then format (e.g., “IF I am tempted to skip exercising, THEN I will tell myself no excuses and remind myself I will feel great after exercising”) and asked to make their own plans using the if-then format. Participants will then be presented with their plan and asked to repeat it to themselves several times. A record of the plan will be automatically emailed to the participant and saved in their plan repository. When participants have finished Module 1, they will be presented with the first page of Module 2 (“Eating fruit and vegetables”), and instructed to work through the module in the same way as with Module 1 (i.e., they read theory-based messages before being asked to form a plan). Participants will then be invited to complete Modules 3 (“Avoiding binge drinking”) and 4 (“Avoiding smoking”).

When all four modules have been completed, participants will be given access to the full U@Uni website. The home page will contain an introductory video and text on how to use the website. Tabs will direct participants to the messages and information on each of the four health behaviours as well as links to the planner, their saved plans, and general health information. Participants will have full control over which parts of the intervention website they access and the website will be available during the full duration of the trial.

## Biochemical Analyses

200 participants (100 from each arm of the trial) will be recruited into a further study on the biochemical markers of health-related behaviour. All participants will be sent an email at the start of “Freshers’ Week” inviting them to participate in the study in which they will be required to provide two hair samples that can be analysed for biochemical markers of health-related behaviour. The first hair sample (baseline) will be taken during “Freshers’ Week” and the second (follow-up) taken six months after starting university.

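### Opt-in to the hair sub-study comes after randomisation and first direction to the intervention, so uptake can differ by arm and its 'baseline' sample is not a pre-randomisation measure

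*Protocol*

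**What the plan says.** The order of events has to be put together from four sections of the protocol and Table 1.

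- **Background:** "the initial recruitment emails will be sent to potential participants four weeks before the start of the first semester", which the protocol equates to three weeks before Freshers' Week. The stated aim is to "ensure that potential participants are able to complete the baseline questionnaire well before starting university".
- **Recruitment, Randomization and Allocation:** on completing that questionnaire, participants will "be randomly allocated to one of two arms using a random number generator" within LifeGuide.
- **Intervention:** "After completing the baseline questionnaire, participants in the intervention arm will be directed to the online intervention". This consists of a self-affirmation task and four modules (exercise, fruit and vegetables, binge drinking, smoking), after which "the website will be available during the full duration of the trial".
- **Biochemical Analyses:** 200 people, 100 from each arm, are to be recruited. All participants are emailed at the start of Freshers' Week, "inviting them to participate in the study in which they will be required to provide two hair samples". "The first hair sample (baseline) will be taken during" Freshers' Week "and the second (follow-up) taken six months after starting university".
- **Table 1:** hair samples are entered in the baseline column, beside questionnaire measures that do precede the random draw.

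Sample Size Calculations gives 100 participants for d = 0.40 at alpha .05 and power .80. The protocol describes no agreement to hair sampling before randomisation, no separate randomisation for the sub-study, and no step to balance those who enter it.

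**The concern.** Two things follow from the order of events.

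First, when the hair invitation arrives, people in one arm have been directed to a programme that asks them to plan healthier behaviour, and people in the other have only answered a questionnaire. Each then decides whether to have markers of alcohol, smoking, diet and drug use measured. That decision can depend on arm. If it does, the 100 volunteers in one arm are not exchangeable with the 100 in the other, and randomisation no longer protects the comparison. The fixed quota of 100 per arm would equalise the numbers and could hide a difference in uptake.

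Second, the word baseline suggests a measure taken before allocation. If the hair analysis uses the first sample in that sense, part of any early effect may be subtracted or adjusted away.

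The primary behavioural outcomes are self-reported, so the hair sub-study is the trial's biochemical check on them. A selected comparison would weaken that check.

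**Working it through.** **1. Timeline.**

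| Event | Time relative to Freshers' Week | Protocol section |
|---|---|---|
| First recruitment email | 3 weeks before | Background |
| Questionnaire, random draw, direction to intervention | from 3 weeks before; intended well before arrival | Background; Recruitment, Randomization and Allocation; Intervention |
| Hair invitation and first hair sample | start of the week; during the week | Biochemical Analyses |
| Second hair sample | six months after starting university | Biochemical Analyses |

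The gap between the random draw and the first hair sample is therefore roughly 0 to 3 weeks for those randomised before that week. It is short for late registrants and longest for those who respond as the protocol hopes.

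**2. What comparison is the sub-study powered for?** Inputs: d = 0.40, alpha .05 (two-sided assumed, as sidedness is not stated), power .80.

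n per arm = 2 × (1.960 + 0.842)² / 0.40² = 2 × 7.85 / 0.16 = 98.1, rounded up to 99. The t-test version gives 99.1. The stated 100 reproduces.

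Power with 100 per arm: the standard error of d is √(2/100) = 0.141, so power = Φ(0.40/0.141 − 1.960) = Φ(0.868) = 0.807.

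Power if 100 were the total (50 per arm): the standard error is √(2/50) = 0.20, so power = Φ(2.00 − 1.960) = 0.516.

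So 100 is a per-arm figure, in line with Biochemical Analyses. The planned test compares the arms and needs comparable volunteers.

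**3. Room for selection.** Expected respondents: 5000 × .3134 = 1567. The sub-study takes 200/1567 = 12.8%. This is a recruitment target. It shows that selection is possible, not that it occurs.

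**4. Illustration of selective uptake (assumed; the protocol gives no value).** Suppose there is no intervention effect, but uptake shifts the mean six-month marker in one arm by s standard deviations. With standard error 0.141, the two-sided rejection rate is P(|Z + s/0.141| > 1.960).

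| s | s as share of 0.40 | s/0.141 | False-positive rate |
|---|---|---|---|
| 0 | 0% | 0 | 5% |
| 0.1 | 25% | 0.71 | about 11% |
| 0.2 | 50% | 1.41 | about 29% |

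These are unadjusted figures. Adjustment for prior behaviour would lower them.

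**5. Illustration of the first sample used as baseline (assumed).** Let a share f of a true difference of 0.40 already be present at the first sample.

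- A change score leaves 0.40 × (1 − f). For f = 0.25 this is 0.30, and power with 100 per arm falls from 0.807 to 0.564 (standard deviation held at 1).
- Covariate adjustment with correlation r between the two samples leaves 0.40 × (1 − r × f). For r = 0.5 and f = 0.25 this is 0.35.

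The protocol gives neither f nor r. If f = 0, nothing is lost under either analysis.

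**The case against.** The best defence is that hair has to be taken in person, Freshers' Week is the first practical occasion, and the protocol says openly when the sample is taken. The intervention is about behaviour at university, so a sample in that week falls near the start of the period it targets and may be almost unaffected. That stands in part: it limits how far the first sample is contaminated. It does not answer the selection point, because the invitation, unlike the sampling, could come before the random draw.

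Some stronger readings are tempting, and the documents do not support them.

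- A reader might infer that the trial arms are self-selected. They are not. Allocation is by random number, and only entry to the sub-study is voluntary. Uptake that differs by arm is a risk, not a finding.
- A reader might infer that the intervention is complete by the first hair sample. Delivery has only begun. Website access continues throughout, a prompt is sent shortly before semester 2, and the alcohol and smoking modules come last of the four, so exposure to them by that week is not certain.
- A reader might infer that the analysis removes any early effect. The protocol's adjustment for baseline scores is described for the four targeted behaviours. No hair model is given, and covariate adjustment would remove only part of such an effect.
- A reader might set a shift of 0.1 to 0.2 SD against the main trial's d = 0.20 and call it as large as the whole effect. The relevant benchmark is the sub-study's own 0.40.

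It is also fair to say that the first hair sample, although taken after randomisation, may be the best available covariate for prior level of the same marker. For that reason it should not simply be discarded.

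**Conclusion.** The point holds for the hair sub-study only. Its entrants choose to join after randomisation and after one arm has been directed to the intervention, with no step to protect the comparability of the two groups of 100. For anyone randomised before Freshers' Week, the sample labelled baseline is an early post-randomisation sample.

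The size of either problem cannot be computed from the protocol. It does not state how uptake might differ by arm, what period of exposure the hair reflects, or how fast behaviour would change. The range of 25 to 50% of the target effect rests wholly on an assumed shift of 0.1 to 0.2 SD. The sample size of 100 per arm is not in error, and the four primary outcomes keep their pre-randomisation questionnaire baselines. The change is worth making because no later analysis can restore a recruitment step before randomisation.

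**What to change.** 1. Add one item on interest in hair sampling at the end of the baseline questionnaire, before LifeGuide draws the random number. In Freshers' Week, invite only those who said yes.
2. In Biochemical Analyses and in Table 1, label the first sample early post-randomisation, so that it no longer stands as a baseline measure.
3. Compare six-month hair markers between arms with adjustment for the self-reported behaviours collected before randomisation. Show the result with and without the first hair sample as a covariate. The baseline drug-use item is an indirect count that does not identify individual use, so it offers little adjustment for drug markers.
4. Report, by arm, how many were invited, agreed and gave each sample, with the pre-randomisation characteristics of those who entered.

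Cost: one extra item in a questionnaire the protocol wants to shorten, and a smaller pool from which to find 100 per arm. No visits or assays are added. Attendance still comes after allocation and can differ by arm, so selection is reduced, not removed; item 4 lets a reader see how much may remain.

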## Measures

Primary outcome measures: Self-reported health behaviour will be measured using a mixture of reliable and validated measures as well items from the Health Survey for England (HSE) [5]. (i) *Fruit and Vegetable Consumption.* Fruit and vegetable consumption (portions per day) will be assessed using a two-item dietary questionnaire [6] which has been validated against bio-chemical markers (e.g., potassium excretion, urinary potassium/creatinine ratio and plasma vitamin C). (ii) *Physical Activity.* The International Physical Activity Questionnaire (IPAQ) will be used to assess levels of physical activity. Respondents indicate how many times, and for how long, they have engaged in vigorous exercise, moderate exercise and walking in the past 7 days. These values are then converted into METs (metabolic equivalent of task) to provide a total score. The IPAQ has undergone extensive reliability and validity testing across 12 countries [7]. The IPAQ items will be supplemented by more detailed questions on walking from the HSE. (iii) *Alcohol.* Alcohol consumption will be assessed using a retrospective seven-day diary in which participants are asked to report the amount of alcohol consumed on each of the past 7 days [8]. The total number of units of alcohol consumed in the past week (and the number of binge sessions) will be calculated. (iv) *Smoking.* Items based on the HSE [5] will be used to assess participants’ current smoking status (and the typical number of cigarettes/amount of tobacco smoked).

Secondary outcome measures: (i) *Social cognitive variables.* Brief measures of social cognitive variables for each behaviour will be constructed in line with current recommendations [9]. These will include measures of attitude (e.g., “Engaging in binge drinking at university would be... good/bad”), norms (e.g., “Most people who are important to be think I should/should not engage in binge drinking at university”), self-efficacy (e.g., “If I wanted, I could easily engage in binge drinking at university”), perceived control (e.g., “Whether or not I engage in binge drinking at university is under my control”), intention (e.g., “I intend to engage in binge drinking at university”) and planning (e.g., “To what extent do you have a detailed plan about how to avoid binge drinking at university?”). (ii) *Health status* will be assessed using the EQ-5D-3L [10]. The EQ-5D-3L is a short, standardised measure of health status that assesses levels of severity (no problems/some or moderate problems/extreme problems) in five dimensions: mobility, self-care, usual activities, pain/discomfort, anxiety/depression. The measure provides a descriptive profile and a single index of health status. (iii) *Recreational drug use.* An indirect method of assessing recreational drug use will be used that maintains respondent anonymity [11]. Respondents will be asked to indicate the number of yes answers (0 or 5, 1, 2, 3, 4) to 5 questions – 4 of which have 50% population prevalence (e.g., odd or even date of birth) and 1 of which is on their use of recreational drugs. (iv) The Alcohol Use Disorders Identification Test (AUDIT) [12] will also be used to assess hazardous and harmful patterns of alcohol use. (v) *BMI.* Participants will record their height and weight to calculate BMI. (vi) *Health services usage.* Participants will be asked to report their use of health services (e.g., GP visits, hospitalisations). (vii) *Engagement with the digital intervention.* Various measures of engagement with the intervention will be recorded including the number of pages visited, the number of activities completed, etc.

Hair analysis: For participants who participate in the additional study of biochemical markers of health behaviour, the hair samples will be liquefied and analysed for biochemical markers of various health behaviours related to alcohol consumption, cigarette smoking, diet

and recreational drug use. The participants will also have their height and weight measured to calculate BMI.

